#### **4. STUDY ENDPOINTS AND EVALUATIONS FOR PHASE I COHORTS**

#### 4.1. Study Endpoints

#### 4.1.1. Primary Endpoint

- Assessment of safety and tolerability of Ad-RTS-hIL-12, administered by intratumoral injection plus veledimex administered PO, as determined by the AE rate and the occurrence of DLTs analyzed specifically for each cohort.

#### 4.1.2. Secondary Endpoints

- Determination of the recommended pediatric Phase II veledimex dose when given with intratumoral Ad-RTS-hIL-12 [REDACTED]
- Veledimex PK estimates
- The ratio of the concentration of veledimex in the brain tumor and the blood (Arm 1 only)

---

Confidential

- Investigator assessment of response, including objective response rate (ORR) and progression-free survival (PFS)
- Overall Survival (OS)

[REDACTED]

[REDACTED]

[REDACTED]

#### **4.2. Baseline and Demographic Characteristic Evaluations**

- Demographics
- Baseline characteristics
- Medical history
- Prior therapies/surgeries
  - Surgical history
  - Brain tumor diagnosis
  - Prior cancer treatment
- Concomitant medications/procedures

#### **4.3. Dose Limiting Toxicity (DLT)**

Dose Limiting Toxicities are defined as events that occur during the first 28 days (Day 0 - Day 28) that meets one of the following criteria:

- Any local reaction that requires operative intervention and is felt to be attributable to study drug
- Any local reaction that has life-threatening consequences requiring urgent intervention or results in death and is felt to be attributable to study drug
- Any Grade 3 or higher non-hematologic adverse event that is at least possibly related to study drug and lasts  $\geq 3$  days
- Nausea and vomiting will not be considered a DLT unless at least Grade 3 and refractory to antiemetics
- Grade 3 or higher thrombocytopenia ( $< 50,000/\text{mm}^3$ ) at least possibly related to study drug
- Any Grade 4 hematologic toxicity (except thrombocytopenia) that is at least possibly related to study drug and lasts  $\geq 5$  days

Note: Diagnostic brain tumor biopsy is not considered a DLT.

- Seizures, headache, and cerebral or pontine edema are commonly observed in this population.

- The grade of toxicity will be recorded.
- However, unless a relationship to study drug is documented to be the main contributory factor, the AE will not be considered a DLT.
- Transient neurological changes are expected in Arm 2 and will not be considered a DLT unless they last > 10 days.

#### **4.4. Recommended Pediatric Phase II Veledimex Dose**

The recommended pediatric Phase II veledimex dose will be determined using the Evaluable Safety Population (ESP) which is defined in [Section 5](#).

- The recommended pediatric Phase II dose is defined as the dose level below the dose in which  $\geq 33\%$  of subjects in the same cohort experience DLTs. If 2 DLTs occur in the same cohort, dose escalation will stop in the cohort experiencing the DLTs.

The recommended pediatric Phase II dose will also be determined in the context of variable corticosteroid exposure and will be reported as such.

#### **4.5. Safety Evaluations**

The safety evaluations include:

- Adverse Events (AEs)
- Extent of study drugs exposure
- Treatment compliance and modification
- Clinical laboratory assessments including hematology, coagulation, serum chemistry and urinalysis
- Vital signs including weight
- Physical exams including targeted neurological exam
- Electrocardiogram (ECG)
- Lansky, Karnofsky, and ECOG performance Status
- Pregnancy test

#### **4.6. Efficacy Evaluations**

The secondary efficacy endpoints include Investigator assessment of ORR, PFS and OS. The Investigator assessment of ORR and PFS will be determined for each cohort according to the baseline (Day 2) iRANO assessment, with tumor response characterized by iRANO criteria for adults, pending issuance of pediatric criteria.

The following variables will be used for the determination of tumor response variables and OS by subject ID:

[figure not shown]
- Tumor response by iRANO for
  - Target, non-target and non-enhancing lesions.

- Overall response
- ORR defined as sum of partial responses and complete responses.
- PFS defined as duration of time from first dose of the study drug to the date of disease progression, or death of any causes, whichever occurs earlier, plus 1 day.
- OS defined as the duration of time from first dose of the study drug to the date of death. Subjects who are still alive 2 years after first doses of study drug will be censored at the last follow up contact date.

#### **4.7. Pharmacokinetic Assessment**

Veledimex PK parameters will be determined based on blood (plasma) levels of veledimex using WinNonLin Phoenix 64 and will include, but are not limited to, the maximum plasma concentration, time to maximum plasma concentration, and area under the curve. The PK analysis will be described in a separate analysis plan.

Only PK concentrations will be summarized in this SAP.

A large rectangular area of the page is completely blacked out, indicating redacted content.

### **5. ANALYSIS POPULATIONS AND APPLICATIONS**

#### **5.1. Enrolled Population (EP) including Screen Failures**

- The EP includes all subjects who signed an informed consent who were subsequently evaluated for eligibility.
- Subjects screened for eligibility and not treated are denoted as Screen Failures.
- Screen Failures are subjects who signed an informed consent and subsequently:
  - Did not meet the eligibility criteria of the protocol, or,
  - Withdraw consent to be treated before receiving any experimental treatment.

The number of subjects who were screened and not treated will be described in the subject disposition where applicable.

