Immediately after tumor resection, Ad-RTS-hIL-12 [REDACTED] will be administered by [REDACTED] injection into approximately two sites within the residual tumor for a total volume of 0.1 mL. The total amount delivered to each site will be recorded in the electronic case report form (eCRF). If less than the planned total injected volume is administered, the reason will be provided. Care should be taken to avoid intraventricular or basal cisternal injection or other critical locations. The day of Ad-RTS-hIL-12 administration is designated as Day 0. When available, an intra-operative magnetic resonance imaging (MRI) scan should be performed to guide the Ad-RTS-hIL-12 injection to areas of contrast-enhancing tumor tissue.

After the Ad-RTS-hIL-12 injection, veledimex will be administered PO once daily (QD) for 14 days. The first postresection veledimex dose is to be given on Day 1, preferably in the morning and within approximately 30 minutes of completion of a regular meal. There should be a minimum of 10 hours between veledimex doses. Subsequent veledimex doses (Days 2 to 14) are to be taken at approximately the same time of day (± 1 hour) as the Day 1 dosing and within approximately 30 minutes of completion of a regular meal.

Arm 2: Subjects with DIPG who will NOT undergo tumor resection

Subjects with DIPG who will not undergo tumor resection will receive Ad-RTS-hIL-12 by standard stereotactic surgery on Day 0. At the time of stereotactic surgery, prior to Ad-RTS-hIL-12 injection, brain tumor biopsy and blood samples will be collected.

Ad-RTS-hIL-12 [REDACTED] will be administered by stereotactic injection into the intratumoral site. The day of Ad-RTS-hIL-12 administration is designated as Day 0. The total amount delivered to each site will be recorded in the eCRF. If less than the planned total injected volume is administered, the reason will be provided. Care should be taken to avoid intraventricular or basal cisternal injection or other critical locations.

After the Ad-RTS-hIL-12 injection, veledimex will be administered PO QD for 14 days. The first veledimex dose is to be given on Day 1, preferably in the morning and within approximately 30 minutes of completion of a regular meal. Subsequent veledimex doses (Days 2 to 14) are to be taken QD and at approximately the same time of day (\pm 1 hour) as the Day 1 dosing and within approximately 30 minutes of completion of a regular meal. There should be a minimum of 10 hours between veledimex doses.

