8. SELECTION AND WITHDRAWAL OF SUBJECTS

8.1. Inclusion Criteria

The eligible study population includes pediatric subjects with a) recurrent or refractory supratentorial brain tumors, not in direct continuity with the ventricular system, that are unresponsive to conventional treatment or for which there is no alternative curative therapy (Arm 1) and b) non-disseminated DIPG post prior standard focal radiotherapy and for which a biopsy has previously been obtained (access to results required; access to tissue preferred) (Arm 2).

Inclusion Criteria:

1. Male or female subjects ≤ 21 years-of-age with the demonstrated ability to swallow capsules whole and who are willing to provide access to previously obtained biopsy results
2. Provision of written informed consent and assent, when applicable, for tumor resection, stereotactic surgery, tumor biopsy, sample collection, and/or treatment with study drug prior to undergoing any study-specific procedures
3. **Arm 1:** Evidence of recurrent or progressive supratentorial tumor, which has shown a $> 25\%$ increase in bi-dimensional measurements by MRI or is refractory with significant neuro-deterioration that is not otherwise explained with no known curative therapy, not in direct continuity with the ventricular system (e.g., there is physical separation between the tumor and ventricle, the tumor does not open directly into the ventricular system).
4. **Arm 2:** Clinical presentation of DIPG and compatible MRI with approximately 2/3 of the pons included and without evidence of dissemination. Subjects should be ≥ 2 weeks and ≤ 10 weeks post standard focal radiotherapy (*i.e.*, dose of 5400 to 5960 cGy and maximum dexamethasone of 1 mg/m²/day).
5. At the time of registration, subjects must have recovered from the toxic effects of previous treatments, as determined by the treating physician. The washout periods from prior therapies are intended as follows (windows other than what is listed below should be allowed only after consultation with the Medical Monitor):
 - a. Targeted agents, including small-molecular tyrosine kinase inhibitors: 2 weeks
 - b. Other cytotoxic agents: 3 weeks
 - c. Nitrosoureas: 6 weeks
 - d. Monoclonal antibody immunotherapies (*e.g.*, PD-1, CTLA-4): 6 weeks
 - e. Vaccine-based and/or viral therapy: 3 months
6. On a stable or decreasing dose of dexamethasone for the previous 7 days
7. Able to undergo standard MRI scans with contrast agent before enrollment and after treatment

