8.4. Subject Withdrawal Criteria

The Sponsor may terminate this study at any time. The Investigator and/or the subject have the right to terminate the subject's participation in the study at any time. Efforts should be made to ask subjects who discontinue study drug to be available to complete the follow-up assessments.

A subject **may** discontinue study treatment prematurely for any of the following reasons:

- The Investigator determines further participation is not in subject's best interest (e.g., subject experiences rapid clinical deterioration in the absence of confirmed disease progression)
- Subject has confirmed disease progression

A subject **MUST** discontinue study treatment in the event of any of the following:

- Subject request to end study treatment
- Any treatment-related AE(s) that meet withdrawal criteria
- Substantial noncompliance with study requirements
- Confirmed positive pregnancy test
- Any intercurrent illness that would, in the judgement of the Investigator or Sponsor's Medical Monitor, affect assessments of clinical status to a significant degree and require discontinuation of protocol therapy

A subject **MUST** be withdrawn from the study in the event of any of the following:

- Withdrawal of informed consent for the study
- Ad-RTS-hIL-12 injection was not injected

Every effort should be made to follow subjects who withdraw from study treatment for ongoing treatment-related AEs until resolved, no resolution is expected, or the study has ended.

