10.2. Veledimex Administration and Timing

In Arm 1, the first veledimex dose will be taken before administration of Ad-RTS-hIL-12 (3 hours \pm 2 hours) on Day 0 on an empty stomach (excluding other medications), before craniotomy and tumor resection. After the initial dose of veledimex, subjects will continue QD veledimex for an additional 14 days. Subjects in Arm 1 will receive up to a total of 15 veledimex doses.

In Arm 2, the first veledimex dose will be taken the day after administration of Ad-RTS-hIL-12 (*i.e.*, on Day 1). After the initial dose of veledimex, subjects will continue QD veledimex for an additional 13 days. Subjects in Arm 2 will receive up to a total of 14 veledimex doses.

In both study Arms, veledimex doses (Days 2 to 14) are to be taken QD and at approximately the same time of day (\pm 1 hour) as the Day 1 dosing and within approximately 30 minutes of completion of a regular meal. There should be a minimum of 10 hours between veledimex doses.

All veledimex doses will be recorded and safety monitored. If Ad-RTS-hIL-12 injection is not performed, subjects will not receive subsequent veledimex dosing.

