16.4.2. Safety Analyses

For the first veledimex dose cohorts in Arms 1 and 2 (*i.e.*, Cohorts 1 and 3, respectively), a minimum of three ESP subjects must be eligible for evaluation of safety. In addition, evaluation of any DLTs will be performed according to protocol-defined criteria. Safety variables will be tabulated and presented by arm and by dose cohort.

Safety evaluations will be based on the incidence, intensity, and type of AEs and SAEs. Clinically significant changes in the subjects' physical examinations, vital signs, ECG evaluations, and abnormal laboratory values will be captured as AEs. Safety will also be assessed based on medical history and prior/concomitant medications.

The safety evaluation period extends from the date the subject signs the ICF or assent form, as applicable, through the Initial Follow-up Period (Day 56), unless the subject discontinues from active follow-up due to one of the following reasons:

- Symptomatic deterioration also denoted symptomatic progression
- Loss to follow up
- Noncompliance with the protocol
- Other reason not listed above

Exposure to study drug(s) and reasons for discontinuation of study treatment will be tabulated. All treatment emergent- AEs (TEAEs) will be coded according to the System Organ Class and Preferred Term using the Medical Dictionary for Regulatory Activities (MedDRA). The TEAEs will be tabulated by number and percent of subjects according to relationship to the study drug(s), severity, and seriousness. A TEAE is defined as any AE that occurs during or after administration of the first dose of study drug through the evaluation period for safety defined above, regardless of relationship to study drug; or any event that is present at baseline that worsens in intensity or is subsequently considered to be drug related by the Investigator. Deaths, SAEs, and AEs resulting in study discontinuation will be listed.

After the conclusion of the safety evaluation period is triggered by a discontinuation event, the subject continues to be followed only for OS.

Laboratory parameters will be summarized by visit. Listings of vital signs and physical examination data will be listed by visit.

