## **5.2. Full Analysis Set (FAS) or the Overall Safety Population (OSP)**

The Full Analysis Set (FAS) or the OSP includes every subject who received at least one dose of any study drug recorded in the Data Management (DM) database excluding screen failures.

- The data analysis for Adverse Events or other Safety variables will be performed on the OSP.
- In the event, the phase II component of the study is implemented and a prespecified null hypothesis comparing study treatment in DIPG subjects with either historical control assumptions or an external control is likely, the primary analysis of OS will be based on the OSP population.

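### The SAP's adverse event outputs omit an Arm 2 child harmed in the Day 0 operation before the injection, because that child has received no study drug

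*SAP*

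**What the plan says.** **Order of events in Arm 2.** The protocol summary states: "At the time of stereotactic surgery, prior to Ad-RTS-hIL-12 injection, brain tumor biopsy and blood samples will be collected". Arm 2 eligibility already requires a tumor "for which a biopsy has previously been obtained" (protocol 8.1), so the Day 0 sample is a study procedure and not the diagnostic biopsy. Protocol 10.2 adds: "In Arm 2, the first veledimex dose will be taken the day after administration of Ad-RTS-hIL-12", and "If Ad-RTS-hIL-12 injection is not performed, subjects will not receive subsequent veledimex dosing".

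**Withdrawal.** Protocol 8.4 makes withdrawal from the study mandatory when "Ad-RTS-hIL-12 injection was not injected".

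**Analysis sets.** SAP 5.2 says the OSP "includes every subject who received at least one dose of any study drug recorded in the Data Management (DM) database excluding screen failures"; protocol 14 and 16.1 also require at least one dose of either component. SAP 5.2 performs the AE and other safety analyses on the OSP, and SAP 13.1 uses it for both the treatment-emergent AE (TEAE) outputs and the AE and SAE listings. SAP 11 bases dose-limiting toxicity outputs on the Evaluable Safety Population, a subset of the OSP.

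**Screen failures.** One bullet of SAP 5.1 reads "Subjects screened for eligibility and not treated are denoted as Screen Failures". The next gives only two reasons: ineligibility, or consent withdrawn before treatment. SAP 9 counts screen failures in disposition only.

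**Collection.** Table 1 footnote f and protocol 14.5 have procedure-related events before dosing recorded as AEs. Protocol 14.7 has every death or SAE from consent to Day 56 sent to the sponsor within 24 hours. Protocol 16.4.2 starts the safety evaluation period at consent or assent.

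**The concern.** The primary endpoint is the safety and tolerability of the vector given by intratumoral injection plus oral veledimex. For an Arm 2 child the route to that injection is an operation on the pons that includes a study biopsy. If that operation goes badly enough for the injection to be abandoned, the adverse outcome itself keeps the child out of the analysis set. The omission can therefore only make the reported safety of the procedure look better.

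The rule also works unequally between arms. An Arm 1 subject takes veledimex before the craniotomy, so one who is harmed in surgery and not injected is already in the OSP. The same kind of event in Arm 2 is not counted. Yet protocol 16.4.2 presents safety by arm and cohort, and Phase I cohorts hold only 3 to 6 subjects, where one child changes the picture.

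**Working it through.** The plan states no figure for this, so the main check is a trace through the rules.

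**Trace for one Arm 2 child: biopsy done, harm occurs, injection abandoned**

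| Step | Source | Result |
|---|---|---|
| Vector given? | the case supposed | No |
| Veledimex given before the operation? | protocol 10.2 (starts Day 1) | No |
| Veledimex given afterwards? | protocol 10.2 | No |
| Doses of any study drug | sum of the above | 0 |
| In the OSP? | SAP 5.2; protocol 14, 16.1 | No |
| In the Evaluable Safety Population? | SAP 5.3 | No |
| TEAE tables; AE and SAE listings | SAP 13.1 (OSP) | Omitted |
| Dose-limiting toxicity outputs | SAP 11 | Omitted |
| Disposition | SAP 5.1, 9 | Screened and not treated, if the broad bullet applies |
| AE recorded? | Table 1 footnote f; protocol 14.5 | Yes, if judged procedure-related |
| SAE sent to sponsor? | protocol 14.7 | Yes |

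For an Arm 1 subject in the same position the dose count is 1 (veledimex before craniotomy), so the subject is in the OSP and the event is listed.

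The SAP also bases some listings on the Enrolled Population, which would include this child: medical history (10.2), prior therapies (10.3) and performance status (13.8). None is an AE listing.

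**How often it could happen.** The documents give no rate of harm leading to an abandoned injection. Assume p between 1% and 5% per operation. The Arm 2 maximum is two cohorts of 6 plus an expansion of 30: 6 + 6 + 30 = 42. (SAP 2.2.2 mentions 30 to 35 for the expansion; the protocol's 30 is used here.)

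- Expected number = n × p: 42 × 0.01 = 0.42; 42 × 0.05 = 2.1.
- P(at least one) = 1 − (1 − p)^n.
- n = 42: 1 − 0.99^42 = 0.344; 1 − 0.95^42 = 0.884.
- n = 12 (both Phase I cohorts, no expansion): 1 − 0.99^12 = 0.114; 1 − 0.95^12 = 0.460.

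**What one such child would change.** This supposes that the event has happened. Intervals are exact (Clopper-Pearson) 95%.

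| Group | Dosed subjects only | Operation started |
|---|---|---|
| Cohort of 3 | 0/3: 0% (0 to 70.8%) | 1/4: 25% (0.6 to 80.6%) |
| Cohort of 6 | 0/6: 0% (0 to 45.9%) | 1/7: 14.3% (0.4 to 57.9%) |
| Expansion of 30 | 0/30: 0% (0 to 11.6%) | 1/31: 3.2% (0.1 to 16.7%) |

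**The case against.** The best defence is that the endpoint concerns the vector plus veledimex. A child given neither says nothing about drug toxicity, and a safety set defined by at least one dose fits that endpoint. This stands as a reason to leave the OSP as it is. It does not justify having no output for harm from a study operation.

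Nor are the data lost. Procedure-related events before dosing are AEs, and SAEs reach the sponsor within 24 hours with follow-up to resolution. Protocol 16.4.2 also says that deaths, SAEs and AEs resulting in study discontinuation will be listed, and that sentence names no dosed set. All this stands. The position is therefore that the protocol can be read as covering this child while the SAP's specified outputs do not.

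Three stronger readings are tempting, and the documents do not support them:

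- *The child is definitely a screen failure.* SAP 5.1 contradicts itself. An eligible, registered child fits the broad bullet but neither of the two listed reasons. The exclusion does not need the label; zero doses is enough.
- *The event disappears from all reporting.* The collection and sponsor-reporting rules, and the listing sentence in protocol 16.4.2, rule this out.
- *Biopsy complications are also lost in injected children.* Protocol 16.4.2 says "A TEAE is defined as any AE that occurs during or after administration of the first dose of study drug", so an event that begins before injection is not a TEAE on timing alone. But it becomes one if it worsens or is later judged drug related, and SAP 13.1 lists all AEs for OSP subjects, not only TEAEs.

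**Conclusion.** The gap is real but narrow. An Arm 2 child harmed in the Day 0 operation and therefore not injected is outside the OSP, and so is missing from the AE tables and the AE and SAE listings that the SAP specifies. It is a gap in tabulation, specific to Arm 2, and at odds with a protocol safety period that begins at consent. SAP 5.1 leaves the child's disposition unsettled.

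The exclusion follows from the documents' rules and needs no assumption about rates. The 34% to 88% chance of at least one such child does: it rests on an assumed 1% to 5% rate with no anchor in the documents, and on all 42 Arm 2 operations taking place. With only the two Phase I cohorts it is 11% to 46%. The unequal treatment of the arms is a matter of rule: SAP 2.1.1 reports Arm 1 concluded with three subjects, and nothing here suggests that any of them was affected.

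The change is worth making because it is cheap and the omission can run in only one direction.

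**What to change.** 1. In the SAP, add one listing and count, by arm and cohort, of AEs, SAEs and deaths from the start of the Day 0 operation, for every subject in whom it was started, injected or not. Keep the OSP definition for the drug-safety tables.
2. In SAP 5.1 and 9, add a disposition category for subjects whose Day 0 procedure was started but who were not injected. Make the two screen-failure bullets agree, so that such subjects are counted apart from screen failures.
3. Reconcile the mandatory withdrawal in protocol 8.4 with the AE and SAE reporting period to Day 56 in protocol 14.7 and 16.4.2, so that sites know what is recorded for an un-injected child after withdrawal.

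The cost is SAP wording, one extra output and one clarification in the protocol. The data needed are already due to be collected, subject to item 3. The downside is a slightly less favourable safety report if such an event occurs. The SAP's version table ends at Draft 2 and SAP 2.2.1 shows Cohort 3 enrolling and Cohort 4 still to come, so on that status the change can be made before database lock.
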